7.4 Analysis Population

The analysis of the primary and secondary endpoints will include all subjects who achieve a successful implant, which is defined as leaving the catheterization lab with a device implanted in the PDA. If a subject has multiple devices attempted during the same procedure, but leaves procedure with at least one device within the PDA the procedure is considered successful. Subjects without an implanted device in the PDA will be excluded. Additionally, subjects who had no follow- up visits up to the six-months +/- one-month window, or lost to follow-up will be excluded.

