Effectiveness Endpoint: The effectiveness endpoint is the rate of effective closure of the PDA using a transcatheter device within six months post procedure. If more than one attempt is required, or multiple devices are required during the same procedure, it is still considered effective if there is Grade 0 or Grade 1 shunt, as defined below, at follow-up (within six months) by transthoracic echocardiography (TTE) or if a second procedure is not required following the initial attempt. If there is device embolization, adjacent vessel stenosis that required retrieval of the device and replacement during the same procedure with less than Grade 1 shunt during follow-up, it is still considered effective. Conversely, if an AE is noted after the procedure that requires a second procedure for treatment that results in greater than Grade 1 shunt, then the procedure is considered not effective, even if the initial attempt was effective.

PDA shunt definition:

Grade 0—none;

Grade 1—trivial (narrow jet adjacent to the device via the PDA). Note: the presence of flow via existing or newly formed aortopulmonary collaterals should not be considered as representing a shunt via the PDA. (See references in **Appendix B** by Skinner and Acherman)

Grade 2—mild (broader jet filling proximal left pulmonary artery branch and extending to main pulmonaryartery);

Grade 3/4—moderate to severe (wide jet filling the main pulmonary artery and extending to pulmonary valve or distal pulmonary artery branches, which also may be accompanied with the presence of flow reversal in the abdominal aortic Doppler pattern during diastole)

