4 STUDY PROCEDURES

The indication to choose transcatheter PDA closure is at the discretion of the referring and implanting physician. No deviation of standard clinical practice is expected to participate in this study. No special pre-procedure, post-procedure, and follow-up testing is required for the purpose of this clinical study.

Enrolled subjects (as defined in section 3.1) will undergo a PDA closure procedure with the appropriate device size deemed suitable for that particular patient. Post-procedure, the subject will need a follow-up within 48-hoours, 1-month and 6-months after the procedure. The Principal Investigator should arrange for appropriate care of subjects following study completion.

This will be a prospective data input Registry. Screen fail subjects who do not have a PDA closure attempt or those who have the Amplatzer Piccolo Occluder device introduced but do not retain an

Amplatzer Piccolo Occluder PDA closure device at the end of the procedure will be noted in the Registry and followed for 48 hours postprocedure.

The following sections provide a detailed description of procedures required by this clinical study.

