4.4 Post-Procedure Follow-up

The follow-up assessment must be obtained within 48-hoours, 1-month and 6-months after the procedure. The schedule of all assessments is provided in Appendix E. The following post-procedure follow-up assessments, diagnostic tests and evaluations and must be included in the PDA module:

- a. Demographics- including subject's age, weight
- b. Transthoracic echo (TTE) including checking for the presence of the device within the PDA, degree of residual shunting if any, spectral Doppler findings, estimates of pulmonary

hypertension, left ventricular function and dimensions, pulmonary and aortic flow and dimensions, pulmonic and tricuspid valve regurgitation

Subjects should be on appropriate endocarditis prophylaxis according to the American Heart Association recommendations for prophylaxis.

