A subject will be considered 'Lost to Follow-up' after two missed scheduled visits within the 6month window, a minimum of two unsuccessful phone calls from investigational site personnel to the subject. These two phone calls must be documented in the subject's research records. If the subject is deemed lost to follow-up, a certified letter will be sent to the subject's last known address or to the subject's general practitioner (GP). A copy of the letter must be maintained in the subject's research records.

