7.2 Primary Effectiveness Endpoint

The primary effectiveness endpoint is the rate of effective closure of the PDA among subjects with a successful device implant as assessed by the presence of either a Grade 0 or Grade 1 shunt (see **Appendix A** for definition) at the 6 month follow-up visit by transthoracic echocardiography.

The proportions of subjects who have effective closure of the PDA at follow-up will be calculated along with the 95% confidence interval. The numerator for the event rate is the number of subjects who have effective closure of the PDA at follow-up. The denominator is the number of subjects in the analysis population (As detailed in Section 7.4). The primary effectiveness endpoint will be compared with the rate reported in the ADO II AS and Continued Access Protocol studies.

Among subjects successfully implanted with any device, the PDA occlusion rate is estimated to be approximately 99%.

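### Successful implant means any device left in the PDA, while infants who do not retain a Piccolo are followed for only 48 hours, so closures with another occluder count as implant successes and can enter the endpoints without six-month data

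*Protocol*

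**What the plan says.** The introduction and Section 1.2 present a study of the Amplatzer Piccolo Occluder, and Sections 7.1 and 7.6 plan a comparison with the earlier Piccolo studies. The definitions behind the analyses are wider.

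- **Section 7.4** bases the primary and secondary analyses on a successful implant, "which is defined as leaving the catheterization lab with a device implanted in the PDA". If several devices are attempted and the infant "leaves procedure with at least one device within the PDA the procedure is considered successful".
- **Section 7.4, exclusion:** "subjects who had no follow- up visits up to the six-months +/- one-month window, or lost to follow-up will be excluded".
- **Section 7.2:** "Among subjects successfully implanted with any device, the PDA occlusion rate is estimated to be approximately 99" percent.
- **Section 2.1:** "The effectiveness endpoint is the rate of effective closure of the PDA using a transcatheter device within six months post procedure".
- **Section 7.5(a)** reports implant success by the Section 7.4 definition over all subjects entered in the PDA module.
- **Section 4** does name the device. Its rule for infants in whom a Piccolo was tried and none was left in place ends as follows: "Amplatzer Piccolo Occluder PDA closure device at the end of the procedure will be noted in the Registry and followed for 48 hours postprocedure".
- **Section 4.4:** "The follow-up assessment must be obtained within 48-hoours, 1-month and 6-months after the procedure".
- **Section 6** (Study Completion): "A subject will be considered 'Lost to Follow-up' after two missed scheduled visits", together with unsuccessful telephone contact.

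**The concern.** Section 4 sorts infants by whether they keep a Piccolo. Section 7.4 sorts them by whether they keep a device. The two rules part company for one kind of infant: the Piccolo is introduced and removed, and the PDA is then closed with a different occluder. Section 7.4 calls this a successful implant. Section 4 treats it like a screen failure and ends follow-up at 48 hours.

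The protocol leaves room for such cases. The adverse event form in Appendix D codes retrieval followed by occlusion with another device, and the case report form in Appendix C has a type field for each of up to four implanted devices.

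Two things are at stake. The implant success rate of a Piccolo study would credit the Piccolo with another device's result. The endpoints that run to six months could also carry infants for whom no one- or six-month visit is planned.

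**Working it through.** The protocol has no sample-size or power figure to reproduce: 500 is a cap and there is no formal hypothesis. The check is mainly a reading of the rules, followed by an illustration of size.

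**Step 1. Follow the infant through the rules.**

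| Rule | Result for an infant left with only another occluder |
|---|---|
| 7.4, successful implant | Met: a device is in the PDA |
| 7.5(a), implant success | Counted as a success; no follow-up exclusion applies |
| Section 4, follow-up | Ends at 48 hours |
| 7.4, no follow-up visit up to the six-month window | Literally not met: Section 4.4 and Appendix E list the 48-hour assessment as a follow-up |
| Section 6, lost to follow-up | Not met: no later visit is scheduled, so none is missed |

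The implant success result does not depend on how the follow-up exclusion is read. Entry into the primary and secondary endpoints does.

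**Step 2. Inputs for size.** N = 500 (Section 2), used here as the number analysed. Effectiveness about 99% (Section 7.2). Major complications 4.0 to 10.0% (Section 7.1). The share s of other-device closures is not in the protocol; 1%, 2% and 5% are assumptions. Intervals are exact binomial 95%.

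**Step 3. Implant success.** The overstatement is the number of other-device closures divided by the number entered. With 500 entered, 5, 10 or 25 such infants give 1, 2 or 5 points. The protocol states no expected implant success rate, so only the difference can be given.

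**Step 4. Effectiveness.** At s = 5% there are 475 Piccolo infants, and 0.99 × 475 ≈ 470 are closed. The 25 others can be handled in three ways:

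- counted as closed: (470 + 25)/500 = 99.0% (97.7 to 99.7)
- excluded: 470/475 = 98.9% (97.6 to 99.7)
- counted as not closed: 470/500 = 94.0% (91.6 to 95.9)

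Counted as not closed, the rate is 98.0% at s = 1% (490/500) and 97.0% at s = 2% (485/500). The protocol does not choose among the three. Section 2.1 accepts Grade 0 or 1 at a follow-up within six months, or the absence of a second procedure, which favours counting as closed. Section 7.2 asks for the six-month echocardiogram, which these infants are not scheduled to have. No section says that a missing echocardiogram is a failure.

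**Step 5. Safety and obstruction.** If the other-device infants add to the denominator but contribute no event, a Piccolo rate r reads as r × (1 − s). At s = 5%, 4% reads 0.04 × 0.95 = 3.8% and 10% reads 0.10 × 0.95 = 9.5%, a dilution of 0.2 to 0.5 points. In whole infants the second figure is 48/500 = 9.6%, or 0.4 points below 10%. The obstruction endpoint has no expected rate in the protocol; the same factor of 0.95 would apply. Zero events is an assumption: an infant whose Piccolo was retrieved may have had a procedural event, which would be seen within 48 hours.

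**The case against.** **The device in Section 7.4 may simply mean the Piccolo.** Section 1.2 limits data entry to procedures in which a Piccolo is attempted. The reference to any device in Section 7.2 stands in a sentence about an expected rate, not in the endpoint definition. Several devices may mean a second Piccolo or another size, and the adverse event form does not say that a replacement is of another type. This has force. A reader might infer that the protocol sets out to pool other occluders with the Piccolo, and the text does not show that intention. It does leave the definition open, and Section 4 shows that the authors could name the Piccolo when they wished to.

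**The exclusion may require a visit inside the six-month window.** Infants released at 48 hours would then leave the primary and secondary endpoints. That reading is possible, though the wording does not say it, and it leaves implant success in Section 7.5(a) untouched.

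**The numbers may be very small.** Section 7.6 says that no device had been approved for this weight group until now, and the study is descriptive. Both points stand and limit the weight of the finding.

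**The statistical analysis plan could settle it.** It could settle the classification. It could not supply visits that Section 4 does not schedule.

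**Conclusion.** The conflict is in the text. Under Sections 7.4 and 7.5(a) a closure with another occluder counts as an implant success in a study of the Piccolo. On the literal wording of the exclusion, such an infant can also enter the primary and secondary endpoints with no planned one- or six-month data.

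The size is unknown because the share is not given. Implant success is overstated by exactly that share of entered infants. For safety and obstruction the likely effect is a small dilution, about 0.2 to 0.5 points on a 4 to 10% major event rate, assuming a 5% share and no events from these infants.

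A reader might infer that effectiveness would fall to 94% or so, or that the reported rates would cease to describe the Piccolo. The protocol supports neither. The first needs a rule, found nowhere in the document, that a missing echocardiogram counts as not closed. The second is out of proportion to the shifts that can be shown. The point deserves correction because the stated rule gives the wrong implant success figure and rewording is cheap.

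**What to change.** - In Sections 2.1, 7.2, 7.4 and 7.5(a), define successful implant as leaving the procedure with at least one Amplatzer Piccolo Occluder in the PDA. Use it for implant success and effectiveness.
- Count infants left with only another device as Piccolo implant failures, and list their outcomes separately.
- Do not carry this restriction into the safety endpoint. It would remove infants whose Piccolo embolised or was retrieved and replaced, although Section 7.1 counts events from an attempted implant. Keep infants with an attempted Piccolo in the numerator and denominator, or report their events alongside the endpoint and state that they were observed for 48 hours.
- Reconcile the follow-up length in Section 4 with the population analysed, and say in Section 7.4 whether the 48-hour contact alone satisfies the follow-up requirement.

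The definition changes cost wording only, since the case report form already records device type and outcome for each device. Reported implant success may be slightly lower.

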7.1 Primary Safety Endpoint

The primary safety endpoint is the rate of major adverse events through up to six-months after an attempted device implant (refer to **Appendix A** for definition).

The proportion of subjects experiencing a major AE through up to six-months will be estimated. The 95% confidence interval for the percent of major AE will be calculated using the exact binomial method. The numerator for the event rate is the number of subjects who experienced an event through up to six-months. The denominator is the number of subjects in the analysis population (As detailed in Section 7.4). The primary safety endpoint rate will be descriptively compared with the rate reported in the Amplatzer Piccolo Occluder IDE and Continued Access Protocol studies. The overall estimated rate for major complications based on published literature ranges between 4.0 to 10.0%.

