8.2 Safety reporting

Safety surveillance within this study (and the safety reporting performed by the investigator), starts as soon as the subject is referred for PDA closure. The safety surveillance and the safety reporting will continue until the follow-up visit has been performed, the subject is deceased, the subject/investigator concludes his/her participation into the clinical study or the subject is deemed lost to follow-up. All adverse event data required to be reported will be collected throughout the clinical study and will be reported to the CCISC PDA Module PI.

For the purposes of this clinical study the following events will be reported (see **Appendix A** for definitions):

- a. Unanticipated adverse device effects
- b. All adverse events viewed/interpreted by investigator to be potentially related to either i) the implant procedure or ii) the device regardless of seriousness

Note – If relatedness is unknown or cannot be determined, then the event must be reported.

Note – if a procedure is abandoned and surgical ligation is used to close the PDA, adverse events associated with the surgical ligation will not be reported.

Records relating to the subject's subsequent medical course must be maintained and submitted (as applicable) to the CCISC PDA Module PI until the event has subsided or, in case of permanent impairment, until the event stabilizes and the overall clinical outcome has been ascertained. Adverse events will be monitored until they are adequately resolved. The status of the subject's condition should be documented at periodic intervals.

Subject deaths will be documented and reported to the CCISC PDA Module PI as soon as possible (but no later than 3 business days) after becoming aware of the event via the applicable CRF. If an unanticipated adverse device effect occurs, the investigator must notify the CCISC PDA Module PI and the IRB immediately, but no later than 10 working days of the investigator's knowledge of the event, as required by 21 CFR §812.150. The CCISC will take any steps necessary to investigate the event, and, as appropriate, will be responsible for notifying FDA and all other participating IRBs and investigators.

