The adverse event is related to the study device/procedure – i.e. an event that follows a reasonable temporal sequence from administration of the study intervention, follows a known or expected response pattern to the suspected intervention, that is confirmed by improvement on stopping and reappearance of the event on repeated exposure and that could not be reasonably explained by the known characteristics of the subject's clinical state.

In summary, the AE is related to any study device or procedure if the event satisfies all of following criteria:

- a. Has a reasonable temporal relationship to intervention (e.g. device implant)
- b. Could not readily have been produced or explained by the subject's clinical state or have been due to environmental or other interventions
- c. Follows a known pattern of response to intervention
- d. Disappears or decreases with reduction in dose or cessation of intervention and recurs with re-exposure

MajorComplication

Major complications are defined as device or procedure-related adverse events resulting in any of the following:

- a. Death
- b. Life-threatening adverse event,
- c. Persistent or significant disability/incapacity, and/or
- d. A major open surgical intervention which is performed by a surgeon under general anesthesia

Examples of Major Complications:

- a. Device or procedure related events leading to death
- b. Cardiac perforation requiring percutaneous (e.g., pericardiocentesis) or open surgical intervention
- c. Cardiac tamponade
- d. Embolization requiring open surgical procedure (e.g., open heart surgery or femoral vessel cut down procedure) to retrieve the device
- e. Persistent hemodynamic instability requiring emergency cardioversion/defibrillation therapy or emergency blood transfusion and/or institution of inotropic therapy
- f. Excessive blood loss or hemolysis requiring transfusion > 20 cc/kg
- g. Persistent or worsening respiratory instability
- h. Cerebral or pulmonary embolism
- i. Persistent cardiac arrhythmia requiring a pacemaker
- j. Arteriovenous fistula requiring open surgical intervention
- k. False aneurysm of the femoral artery requiring surgical intervention
- l. Femoral vessel thrombophlebitis treated with intravenous antibiotics
- m. Infection of the device (bacterial endocarditis)

Minor Complication

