Minor complications are defined as device or procedure-related adverse events that do not fit the definition of a major complication. These will include adverse events which may require medical intervention but are not life threatening, are not likely to have long-term (> 6 months) sequelae, and do not require long term (> 6 months) therapy. The following are examples of adverse events considered to be minor complications:

- a. Embolization that occurs intra-operatively where the device is retrieved using a transcatheter approach (e.g., using a snare) without needing to perform an open surgical procedure, such as open heart surgery or an open femoral vessel cut down procedure.
- b. Reduced peripheral pulse (reversible) that can be managed with anti-thrombotic therapy (e.g., heparin, Aspirin)
- c. Cardiac perforation not requiring percutaneous (e.g., pericardiocentesis) or open surgical intervention
- d. Transient cardiac arrhythmia that is managed successfully with cardioversion or medication
- e. Hematoma of the groin not requiring open surgical intervention

PDA Residual Shunt Grades Definitions

Grade 0—none;

Grade 1—trivial (narrow jet adjacent to the device via the PDA). Note: the presence of flow via existing or newly formed aortopulmonary collaterals should not be considered as representing a shunt via the PDA. (see references in Appendix B by Skinner and Acherman)

Grade 2—mild (broader jet filling proximal left pulmonary artery branch and extending to main pulmonary artery);

Grade 3/4—moderate to severe (wide jet filling the main pulmonary artery and extending to pulmonary valve or distal pulmonary artery branches, which also may be accompanied with the presence of flow reversal in the abdominal aortic Doppler pattern during diastole)

Definitions of significant adjacent vessel stenosis (narrowing/obstruction)

1. Significant obstruction of the left pulmonary artery is defined as less than 30% flow to the left lung by lung perfusion scan or a peak instantaneous gradient in left pulmonary artery ≥35 mmHg by echocardiogram if lung perfusion scan is not available.OR

2. Significant obstruction of the aorta is defined as a gradient of $\geq 20 \text{ mmHg in the aortic}$ is thmus by invasive aortic catheterization or a mean gradient $\geq 20 \text{ mmHg in the aortic}$ is thmus by echocardiogram if invasive aortic catheterization is not available.

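### Primary safety is defined from the attempted implant, but its denominator drops every infant who leaves the lab without a device

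*Protocol*

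**What the plan says.** Protocol Section 7.1 gives the endpoint as follows: "The primary safety endpoint is the rate of major adverse events through up to six-months after an attempted device implant". It then fixes the denominator: "The denominator is the number of subjects in the analysis population (As detailed in Section 7.4").

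Section 7.4 sets a single population for all primary and secondary endpoints, namely infants who leave the catheterization lab with at least one device in the PDA. It adds: "Subjects without an implanted device in the PDA will be excluded". An infant whose first device is removed and replaced in the same procedure stays in. An infant who leaves with none is out, for safety as well as for effectiveness.

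Appendix A lists among major complications "Device or procedure related events leading to death", tamponade, perforation needing intervention, and "Embolization requiring open surgical procedure (e.g., open heart surgery or femoral vessel cut down procedure) to retrieve the device". By contrast, "Embolization that occurs intra-operatively where the device is retrieved using a transcatheter approach" is listed as minor.

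On observation time, Section 4 covers infants in whom a device was tried and none was left in place. Its sentence on them ends: "Amplatzer Piccolo Occluder PDA closure device at the end of the procedure will be noted in the Registry and followed for 48 hours postprocedure". Section 8.2 says "The safety surveillance and the safety reporting will continue until the follow-up visit has been performed", or until death, end of participation or loss to follow-up.

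**The concern.** The safety set is selected on a result of the procedure, and some of the events being counted can bring that result about. An infant who dies during the attempt, or whose device embolizes and is retrieved by open surgery with no device left in the duct, has a major complication and for that reason leaves both numerator and denominator.

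The word used in Section 7.1 does not look like a slip. Section 7.2 expressly conditions effectiveness on a successful implant, and Section 7.5(a) uses everyone entered in the module. The protocol therefore distinguishes these groups elsewhere, and Section 7.4 removes the distinction where it matters most for safety.

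At stake is the figure that Sections 7.1 and 7.6 set beside the IDE and Continued Access results. That comparison is descriptive and the study has no formal hypothesis, so no pass/fail decision turns on it. It is still the study's principal statement about safety in this population.

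**Working it through.** **Inputs from the protocol.** The expected overall major complication rate is 4.0 to 10.0% (Section 7.1). The initial cohort is 500 subjects (Section 2). Intervals are exact binomial at 95% (Section 7.1). The protocol derives no sample size or power, so there is no planning figure to reproduce.

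**Inputs not in the protocol, assumed here.** The share of attempts ending without a device, *f*, is taken as 2%, 5% or 10%. The major-event rate among those attempts, *p_f*, is taken as 20% to 40%, with 0% and equality as checks. The rate among implanted infants, *p_s*, is set at 4%, 7% or 10%, which borrows the protocol's overall range.

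**Formula.** All-attempted rate = (1 − f) × p_s + f × p_f. Section 7.4 reports p_s, so:

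understatement = f × (p_f − p_s).

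This is positive only when failed attempts carry the higher event rate.

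**Results, in percentage points:**

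| p_s | Smallest (f = 2%, p_f = 20%) | Largest (f = 10%, p_f = 40%) |
|---|---|---|
| 4% | 0.02 × 0.16 = 0.32 | 0.10 × 0.36 = 3.60 |
| 7% | 0.02 × 0.13 = 0.26 | 0.10 × 0.33 = 3.30 |
| 10% | 0.02 × 0.10 = 0.20 | 0.10 × 0.30 = 3.00 |

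For the middle value f = 5% at p_s = 4%, the understatement is 0.05 × 0.16 = 0.80 to 0.05 × 0.36 = 1.80 points.

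**Checks on direction.** With p_f = p_s the difference is zero. With p_f = 0 the reported rate is too high: by 0.08 to 0.40 points at p_s = 4%, and by 0.20 to 1.00 points at p_s = 10%.

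**Example in counts.** Take 500 attempts, of which 25 end without a device, and 19 major events among the 475 implanted infants. Section 7.4 reports 19/475 = 4.0% (95% CI 2.4 to 6.2). The all-attempted rate depends on the 25:

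| Events among the 25 | All-attempted rate | Exact 95% CI |
|---|---|---|
| 0 | 19/500 = 3.8% | 2.3 to 5.9 |
| 1 | 20/500 = 4.0% | 2.5 to 6.1 |
| 5 | 24/500 = 4.8% | 3.1 to 7.1 |
| 10 | 29/500 = 5.8% | 3.9 to 8.2 |

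**An ambiguity in the numerator.** Section 7.1 does not expressly restrict the numerator to the Section 7.4 population. Counting events in all attempts over implanted infants only would give, with 5 events among the 25, 24/475 = 5.1%. That is not a proportion of any defined group, and it overstates the 4.8%. Two analysts following the text could therefore report different rates from the same data.

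**The case against.** The strongest reply has four parts.

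*The composite may be narrower.* Section 2.1 limits the safety endpoint to access complications, valve injury, embolization and adjacent vessel stenosis, and counts from the implantation procedure. Death and tamponade are not categories there; they enter through the pointer in Section 7.1 to Appendix A. This is correct, and the two definitions differ. It does not remove the problem, because embolization is in the narrower composite, with outcomes running to surgical retrieval and death. The adverse event form in Appendix D also provides for embolization ending in surgical ligation of the PDA.

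*The size is assumed.* This stands. The 3.6-point maximum implies, in 500 attempts, 18 events among 450 implanted infants and 20 among 50 failures, so that 20 of 38 events fall in failures. Nothing in the protocol supports so extreme a split. Some upper grid points also give an all-attempted rate above the cited 10% (10% + 3.0 = 13%). In the 5-event example the difference is 0.8 points and the intervals overlap heavily. Perforation or tamponade excludes an infant only if no device is left in place.

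*The events are reported elsewhere.* Section 7.5(d) and (e) summarize complications and deaths without an implant restriction. That helps a careful reader, but these are other endpoints with no denominator named, and they do not correct the primary rate.

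*The follow-up statements can be read together.* If infants without a device are outside the six-month analysis, 48 hours of follow-up is consistent with Section 7.4, and Section 8.2 could be read as ending at that visit. This reading is possible, but it leaves the endpoint as worded in Section 7.1 unmet.

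**Conclusion.** The concern holds. Section 7.1 defines one rate and Section 7.4 produces another, and the exclusion that separates them can be caused by the events being counted. This rests on the text alone and needs no assumption.

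The downward direction is likely but not certain: it requires a higher major-event rate in attempts that leave no device. That is plausible where the complication ends the procedure. It is less so where an attempt is abandoned for anatomy or sizing. Under the assumed ranges the understatement is 0.2 to 3.6 percentage points over the whole grid, with the lower and middle values easier to defend than the top. The denominators of the IDE and Continued Access studies are not given, so the effect on that comparison is unknown.

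Section 7.4 also excludes infants with no follow-up visit, which could remove early deaths among implanted infants. That is not counted in these figures.

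**What to change.** In Section 7.4, define a primary safety population of all subjects with an attempted Amplatzer Piccolo Occluder implant, whatever the implant outcome. State what counts as an attempt, and keep screen failures with no attempt out. In Section 7.1, refer to that population for both numerator and denominator, and count every major device- or procedure-related event captured for these subjects. Keep the implanted population for effectiveness and for vessel obstruction; the implanted-only safety rate can be shown beside the primary one.

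Reconcile the 48-hour follow-up in Section 4 with the six-month endpoint in Section 7.1 and the reporting period in Section 8.2, and state how shorter observation enters the primary rate. Align the composite in Section 2.1 with the Appendix A definition used in Section 7.1.

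The cost is small: a wording change and one further analysis set. Section 1.2 already expects data entry for all attempted procedures, so the procedural events should be in the database. The reported rate may become somewhat less favourable. Unless follow-up is aligned, the rate will combine 48-hour and six-month observation, which the report must say.
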